The FRS was developed by Wilson et al in 1998 and has become standard of care for estimating risk of a cardiovascular event over the next 10 years. The estimation takes gender, age, smoking status, systolic blood pressure, total cholesterol and HDL into account when predicting risk (4). Scores are converted into percentage of risk over the next 10 years using a table created by Wilson et al. Individuals with scores of 0-10% are considered low risk. A score of 11-15% indicates low-moderate risk, while a score of 16-20% indicates mod-high risk. Those with scores of >20% are considered high risk, while those with known coronary artery disease or acute coronary syndrome are considered very high risk (2). While the FRS at times is a basis for treatment decisions, this system of calculating risk is not individualized, and does not take into account other contributing factors such as family history, weight, etc.

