CAC scores are reported as a numerical value and a percentage for age that is then regarded in terms of risk categories. A score of zero with no cardiovascular risk factors indicates no evidence of CAD and thus a very low risk of cardiovascular event in the next ten years. If the individual has cardiovascular risk factors with a CAC score of 0, they are considered moderately low risk. A score of 1-100 and a percentage for age percentile less than 75% indicates mild to moderate evidence of CAD and therefore indicates moderately high risk. A score of 101-399 or a percentage for age greater than 75% indicates moderate to high evidence of CAD and therefore is considered high risk with possible current partial blockage of coronary arteries. A score of >400 or any CAC score >100 with a >90% percentage for age indicates extensive evidence of CAD and thus high risk of cardiovascular event in the next ten years and could indicate further testing is needed to address potential majority blockage (9, 10).

A consensus report issued by the American College of Cardiology and the American Diabetes Association emphasizes the concept of a global cardio metabolic risk. Factors that increase the risk of cardiovascular disease include dyslipoproteinemia, hypertension, diabetes and the prediabetic states such as insulin resistance or hyperglycemia, and central obesity. Smoking and sedentary lifestyle exacerbate the risk. The epidemic rise in the prevalence of one or more of these risk factors has created a heterogeneous population at risk that is perhaps not well represented by the traditional Framingham study population, which commenced in 1948.

The American College of Cardiology (ACC) and the American Heart Association (AHA) recognize the incremental benefit of CAC screening and endorse its use in intermediate risk individuals with a FRS between 10-20%. The SHAPE (Screening for Heart Attack Prevention and Education) Task Force report goes further, publishing guidelines calling for the use of CAC scanning or CIMT as part of a nation-wide screening program to detect CAD in males 45 years and older, and females 55 years and older (10).

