Given that the true rates of atherosclerosis within the greater military population are unknown and that the cluster of cardio metabolic risk factors are present at a relatively young age and in greater numbers than the general population, we aim to study the prevalence of subclinical atherosclerosis in US enlisted service members with one or more cardio metabolic risk factor using coronary artery calcium scoring with cardiac computed tomography. While the military has not adopted the SHAPE Task Force guidelines, or any other screening protocol involving imaging based modalities, the value of using risk factors to select individuals who may stand to benefit from the greater predictive power of coronary artery calcium scoring may prove to be useful in this population. This approach could be key to understanding the prevalence of subclinical atherosclerosis, measuring the effect of population health initiatives on rates of atherosclerosis over time and ultimately improving our ability to meet the stated objective of DoD health promotion, which is to return the veteran back to society in relatively good health.

6.2. Hypotheses or Research Questions or Objectives:

Hypothesis: Enlisted military members with 10 or more years of service and at least one cardiovascular risk factor will demonstrate a higher risk of future cardiac events as assessed by coronary artery calcium scoring than the risk calculated by the Framingham Risk Score.

The primary aims of this study are as follows:

- 1) Determine prevalence of atherosclerosis in active duty enlisted military members with 10 or more years of military service and at least one cardiovascular risk factor using coronary artery calcium scoring.
- 2) Assess the rate of reclassification of subjects from one risk category using Framingham Risk Scores (FRS) to another risk category using the results of the Coronary Artery Calcium (CAC) score.
- 3) Compare FRS to the CAC percentage for age risk score for enlisted subjects with at least 10 years of military service and at least one additional cardiovascular risk factor to determine how well the results correlate with one another.

The secondary aims of this study are as follows:

- 1) Compare CAC scores between each group in the following categories to see if there is associations between these categories and formation of calcified plaques:

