 - Coronary Artery Calcium Score Results
 - Framingham Risk Score
 - What the two scores mean
 - Lab Results
 - Lifestyle changes that can be made to decrease risk, i.e. smoking cessation, increasing exercise, dietary changes, etc.
- **For CAC >400:** The study coordinator or other research team member will place a referral into CHCS to the cardiology clinic for further evaluation. At this time a telephone-consult will be placed in the subject’s AHLTA record (See attachment 8 – Telephone Consult Template) and their PCM will be notified via an encrypted e-mail of their CAC results and their referral to cardiology (See attachment 9 – PCM Notification E-Mail Template). If subjects in this category are noted to have abnormal

HgbA1C and/or lipid panel their primary care manager (PCM) will be notified of abnormal results via encrypted e-mail. The HL&VC will contact the subject to schedule a follow-up appointment for the subject to be seen within 30 days, but no later than 60 days of the CAC scan. At the cardiology follow-up appointment, the following will be discussed:

- Coronary Artery Calcium Score Results
 - Framingham Risk Score
 - What the two scores mean
 - Lab Results
 - Lifestyle changes that can be made to decrease risk, i.e. smoking cessation, increasing exercise, dietary changes, etc.
 - Medications that could reduce risk of cardiac events in the future
 - Interventions, imaging or further testing that may be necessary to further evaluate/treat the subject
- **Measurements:**
 - Framingham Risk Score – (See attachment 10 – Framingham Risk Calculation Tables), includes age, systolic blood pressure, HDL level, Total Cholesterol level and smoking status
 - HgbA1C (if not previously tested within 3 months prior to study enrollment)
 - Lipid Panel (if not previously tested within 3 months prior to study enrollment)
 - Coronary Artery Calcium Score
 - Waist Circumference
 - Blood Pressure
 - **Demographic Info to be Collected:**
 - Branch of Military Service
 - Rank
 - Number of Years of Military Service
 - Number of Deployments >2 months
 - Number of Years living on base in Dormitories
 - Number of PT test failures
 - Number of Cardiac Risk Factors (Tobacco use, Diabetes, pre-diabetes, hypertension, waist circumference, hyperlipidemia)

6.5. Intervention/Treatment:

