with 10 or more years of military service. Females do not tend to demonstrate coronary artery calcium in the same manner/degree as males. Therefore an additional pilot sample of 30 female volunteers will be used to assess the prevalence detected in the female active duty population.

Data Analysis

- Primary Aims:
 - Determine prevalence of atherosclerosis in active duty enlisted military members with 10 or more years of military service using coronary artery calcium scoring.
 - A 95% confidence interval will be calculated for the observed prevalence in the active duty population.
 - Assess the rate of reclassification of subjects from one risk category using Framingham Risk Scores (FRS) to another risk category using the results of the Coronary Artery Calcium (CAC) score.
 - For the purposes of this study, the SHAPE guidelines will be used to classify the CAC scores and percentage by age into the following categories:
 - Low Risk: CAC of 0 and no cardiovascular risk factors
 - Low-Moderate Risk: CAC of 0 with cardiovascular risk factors
 - Moderate-High Risk: CAC 1-100 *and* percentile for age <75%
 - High Risk: CAC 100-399 *or* percentile for age >75%
 - Very High Risk: CAC >100 *and* percentile for age >90% *or* CAC >400
 - For the purposes of this study, the FRS percentages will be classified into the following categories:
 - Low Risk: FRS 0-10%
 - Moderate Risk: FRS 11-15%
 - Moderate-High Risk: FRS 16-20%
 - High Risk: FRS >20%
 - Very High Risk: Acute Coronary Syndrome or known Coronary Artery Disease or significant multiple risk factors

This study will assess the rate at which CAC scoring reclassifies the FRS of a subject to a different risk category. To do so a descriptive table will be used to demonstrate the changes seen. The net reclassification improvement (NRI) will be calculated to describe further the amount of reclassification that is accomplished by using the CAC scoring method (19). Please see reference 19 for more information.

- Compare the Framingham Risk Score (FRS) to the Coronary Artery Calcium (CAC) score for enlisted subjects with at least 10 years of military service to determine how well the results correlate with one another.

- Linear Regression model will be used to determine if the FRS score correlates with the CAC score.
- Secondary Aims:

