 - A t-test will be used to compare CAC scores between each group in the following categories to see if there are associations between these categories and formation of calcified plaques:
 - Those meeting the criteria for metabolic syndrome vs. those not meeting criteria (See attachment 1 – Diagnostic Criteria for Metabolic Syndrome).
 - Those who lived in the dorms for >5 years compared to those living in the dorms for <5.
 - Those with PT test failures vs. those without.
 - Analysis of Variance (ANOVA) and/or Logistic regression will be used to compare CAC scores between each group in the following categories to see if there are associations between these categories and formation of calcified plaques:
 - Number of years of military service in the following groups: 10-14 years, 15-19 years 20-24 years and 25+ years
 - Those with 1 risk factor vs. 2 risk factors, vs. 3 risk factors, vs. 4 risk factors, vs. 5 risk factors (as listed in the inclusion criteria section).
 - The correlation between CAC and FRS scores will be described using multiple linear regression for the following categories:
 - Those meeting the criteria for metabolic syndrome vs. those not meeting criteria.
 - Those who lived in the dorms for >5 years compared to those living in the dorms for <5.
 - Those with PT test failures vs. those without.
 - Number of years of military service in the following groups: 10-14 years, 15-19 years 20-24 years and 25+ years.
 - Those with 1 risk factor vs. 2 risk factors, vs. 3 risk factors, vs. 4 risk factors, vs. 5 risk factors (as listed in the inclusion criteria section).

Source of Research Material per Participant:

Source of Research Material per Participant	Standard Care	Research Driven
Blood Sample – Hgb A1C	0	1 **
Blood Sample – Lipid Panel	0	1 **
Cardiac CT Scan	0	1
Outpatient Record Review	0	1
Subject Interview	0	1
Demographics	0	1

** In some subjects, the labs could be standard of care, but since the labs will not be standard of care for all subjects, they are listed here as research driven.

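### Primary aim 3 names the CAC percentage for age in 6.2 but the CAC score in 6.6; on the age-ranked scale, part of any weak correlation with FRS reflects age normalisation

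*Combined protocol and SAP*

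**What the plan says.** - **Objective (6.2, primary aim 3):** "Compare FRS to the CAC percentage for age risk score for enlisted subjects with at least 10 years of military service", to see how well the two correlate.
- **Analysis (6.6, Data Analysis, Primary Aims):** the same aim becomes "Compare the Framingham Risk Score (FRS) to the Coronary Artery Calcium (CAC) score for enlisted subjects with at least 10 years of military service", and the method is "Linear Regression model will be used to determine if the FRS score correlates with the CAC score". The percentage for age is not mentioned under this aim.
- **Secondary analyses (6.6):** "The correlation between CAC and FRS scores will be described using multiple linear regression for the following categories". These also use scores.
- **Inputs to FRS:** 6.1 states "The estimation takes gender, age, smoking status, systolic blood pressure, total cholesterol and HDL into account when predicting risk". The measurement list in 6.4 agrees: "includes age, systolic blood pressure, HDL level, Total Cholesterol level and smoking status".
- **Two CAC scales (6.1):** "CAC scores are reported as a numerical value and a percentage for age that is then regarded in terms of risk categories".

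The documents do not state which wording of aim 3 prevails, which reference population defines the percentage for age, or what percentage a subject with CAC=0 receives.

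**The concern.** FRS is an absolute 10-year risk with age among its inputs. The percentage for age is relative: it places a subject among people of the same age. At equal calcium, a younger man tends to have a lower FRS and a higher percentile. Correlating the two therefore sets a measure that contains age against one from which age has been largely removed, and some of the shared signal is lost by construction.

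The hypothesis in 6.2 is directional: CAC is expected to show higher risk than FRS. A weak correlation under aim 3 could be taken as evidence that FRS misses atherosclerosis in this population, when part of the weakness comes from the scale. Because the two sections name different variables, the choice could also be made after the data are seen. Section 12 lists about four hours of biostatistics support, at the end of data collection.

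**Working it through.** **1. The plan's own figure.** The documents give no correlation, power or precision figure for aim 3. The only sample-size calculation is for prevalence (6.6): n = 1.96² × 0.10 × 0.90 / 0.05² = 138.3, stated as 138, so it is reproduced. With 150 men and 10% dropout, 150 × 0.90 = 135 male completers.

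**2. Simulation of the two scales.** From the documents: men from age 35 (6.7), and CAC prevalence of 10% (6.6) or 20.6% (the Army cohort cited in 6.1). Everything else is assumed:
- 200,000 men per scenario, ages uniform 35 to 55, one standard normal risk factor rf; a third prevalence of 35%.
- log FRS = log 5 + 0.08(age - 42) + 0.5 rf, with FRS capped at 30.
- logit P(CAC>0) = a + b(age - 42) + 0.5 rf, with b = 0.08 or 0.12 and a set to give the prevalence.
- log CAC if positive = 2.5 + 0.08(age - 42) + 0.3 rf + N(0, 1.4).
- Percentile taken within year of age.

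Results over the six scenarios (three prevalences, two values of b), all subjects:

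| CAC variable against FRS | Pearson r |
|---|---|
| log(CAC+1) | 0.24 to 0.41 |
| percentile for age, CAC=0 coded 0 | 0.20 to 0.32 |
| percentile for age, CAC=0 at mid same-age rank | 0.12 to 0.18 |
| raw CAC score | 0.14 to 0.21 |

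With zeros coded 0, the percentile loses 12 to 24% relative to log(CAC+1). In Spearman terms the loss is smaller: 0.20 to 0.39 for absolute CAC against 0.19 to 0.33 for the percentile. With zeros at mid-rank, Spearman's rho reaches -0.46 at 10% prevalence and is near zero at 35%.

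**3. Why the coding of zeros matters.** Suppose 95% of one age group and 75% of an older one have CAC=0 (illustrative figures). At mid-rank, the zeros receive 95/2 = 47.5 and 75/2 = 37.5. Among zeros, who are most of the sample, the percentile then falls with age while FRS rises with age.

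**4. A second model.** A latent-CAC model was run over 4 prevalences (10 to 50%) × 2 age effects × 4 age shares of log-FRS variance (10 to 70%) × 4 risk-factor effects = 128 scenarios, using Spearman's rho in all subjects:
- Zeros coded 0: the percentile lowered rho by a median of 0.03 (maximum 0.14) and never made it negative (0.04 to 0.57).
- Zeros at mid same-age rank: -0.61 to 0.49.
- Zeros at the top of their same-age rank: -0.78 to 0.36.

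At a central setting with 10% prevalence, rho was 0.23 for absolute CAC and 0.22, -0.45 and -0.62 for the three percentile codings. At 20.6% prevalence the values were 0.28, then 0.26, -0.25 and -0.51.

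**5. CAC-positive subjects only (mechanism, not a planned analysis).** In the first model, r with FRS was +0.31 to +0.33 for log CAC and -0.10 to -0.21 for the percentile. In the second, rho for the percentile ranged from -0.44 to +0.31 and was negative in 78% of scenarios; rho for absolute CAC was always positive (0.03 to 0.46).

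**The case against.** The strongest reply is that 6.6 already uses the CAC score, for aim 3 and for the secondary correlations, so the percentile problem never arises if the analysis section governs. That stands as a limit: the attenuation applies only if the objective's wording is followed. It does not remove the conflict, since 6.2 defines the primary aim and neither section defers to the other.

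Second, a reader might infer that poor agreement is built in. The documents and the figures do not support that. With zeros coded 0, the whole-sample correlation stayed positive in every scenario. In simulated samples of 135 at 10% prevalence, the sampling intervals for r almost coincide: 0.01 to 0.40 for the percentile and 0.03 to 0.45 for log(CAC+1).

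Third, a reader might infer that the study will report a reversed sign among CAC-positive subjects. No analysis restricted to them is planned. At 10 to 20.6% prevalence, 135 men would yield about 14 to 28 positives. The 95% half-width for r near zero, tanh(1.96/√(k - 3)), is then 0.53 (k = 14) to 0.37 (k = 28), too wide to tell such values from zero.

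Fourth, the documents do not show that FRS is driven by age. Age is one of several listed inputs, and the point tables are in an attachment that is not shown.

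Fifth, the raw score in 6.6 correlates less with FRS than the percentile does when zeros are coded 0 (0.14 to 0.21 against 0.20 to 0.32). This is correct, so the size of r alone does not condemn the percentile. The case for absolute CAC is that age has not been removed from it and its zero needs no coding rule; the low raw-score r is a reason to use ranks or logs. Finally, asking whether CAC and FRS agree beyond age is legitimate, provided it is presented as that question.

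**Conclusion.** The point holds in a limited form. Sections 6.2 and 6.6 give different CAC variables for one primary aim, and the one in 6.2 is ranked within age while FRS includes age. If 6.2 is followed, the whole-sample correlation is attenuated: modestly with CAC=0 coded as percentile 0 (12 to 24% in Pearson r in one model, a median of 0.03 in rho in the other), and possibly to a negative rank correlation if zeros receive an age-specific rank. The plan leaves that coding open. A weak result would then partly reflect age normalisation. Following 6.6 as written avoids this but leaves a linear regression on a skewed, zero-heavy score.

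The direction of the effect follows from the definitions. The sizes rest on assumed age slopes, risk-factor effects, age range and calcium distribution, and on men only; only the 10% and 20.6% prevalences come from the documents.

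**What to change.** - In both 6.2 (primary aim 3) and 6.6, name the absolute CAC score as the variable compared with FRS.
- Replace the linear regression on the raw score with Spearman rank correlation or regression on log(CAC+1), and report CAC >0 against FRS alongside.
- If the percentage for age is kept, make it secondary. State its reference population and the coding of CAC=0, relate it only to an age-adjusted FRS (for example the partial correlation given age), and label it age-relative.

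The cost is rewording one aim and adding one analysis line. CAC, age and the FRS components are already collected under 6.4.

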 - a. Those meeting the criteria for metabolic syndrome vs. those not meeting criteria (See attachment 1 – Diagnostic Criteria for Metabolic Syndrome)
 - b. Those who lived in the dorms for >5 years compared to those living in the dorms for <5
 - c. Those with PT test failures vs. those without
 - d. Number of years of military service in the following groups: 10-14 years, 15-19 years 20-24 years and 25+ years
 - e. Those with 1 risk factor vs. 2 risk factors, vs. 3 risk factors, vs. 4 risk factors, vs. 5 risk factors (as listed in the inclusion criteria section).
- 2) Compare FRS to CAC cardiovascular risk for each of the following categories:
 - a. Those meeting the criteria for metabolic syndrome vs. those not meeting criteria
 - b. Those who lived in the dorms for >5 years compared to those living in the dorms for <5
 - c. Those with PT test failures vs. those without
 - d. Number of years of military service in the following groups: 10-14 years, 15-19 years 20-24 years and 25+ years
 - e. Those with 1 risk factor vs. 2 risk factors, vs. 3 risk factors, vs. 4 risk factors, vs. 5 risk factors (as listed in the inclusion criteria section)

6.3. Relevance/Significance:

- One of the mottos of the military medical corps is to preserve the fighting force. This concept is essential to the military branches accomplishing their missions. Through public health information and research studies, the military is pushing to change the military culture to support a healthier active force, thus leading to a healthier retiring population. Recognizing the need for further change in the military culture could lead to new policies and support for military members that could reduce the risk of atherosclerosis and heart disease in the future. Of those that died in combat in the Iraq/Afghanistan conflicts, 8.5% demonstrated evidence of atherosclerosis on autopsy (9). Due to higher smoking rates, obesity, MRE consumption, access to fast food on base and stress of deployments, enlisted military members with more than 10 years of military service will likely demonstrate a higher prevalence of atherosclerosis. Understanding the prevalence in this group could lead to changes in health initiatives and could lead to further studies in the future that use CAC scoring to measure the effect of new population health initiatives over time.

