6.7. Subject Population

Age Range: ≥ 18 y/o Children (< 18)

Sex: Male Female

Vulnerable Population: No Yes (explain)

- Children, pregnant women, fetuses, neonates, mentally disabled, and prisoners will not be used in this research study as the population this study is looking at military members with at least 10 years of service. Any females identifying that they may be pregnant will be excluded from the study.

Number of Subjects:

- Total Number of Subjects (nation-wide/study-wide): 180
- Number of Subjects Planned for DGMC: 180
- Number of Subjects Planned for (Specify Institution): 0

Inclusion/Exclusion Criteria:

- **Inclusion Criteria:**
 - Active Duty Military Members with at least 10 years of service
 - Enlisted Rank
 - Males 35 years and older OR Females 45 years and older (please note the age difference is due to the fact that female plaque formation with calcification has been shown to lag that of males by about 10 years)
 - One or More of the Following Risk Factors:
 - **Smoker** – at least 5 pack years in the past 5 years (pack year = number of packs per day * number of years of smoking)
 - **Diabetic** (Fasting glucose of >125 mg/dL on two or more blood draws, or Random Blood Glucose of >200 mg/dL on a single blood draw, or HgbA1C >6.5%, or previous diagnosis of diabetes listed in the subject's medical record) or **Pre-diabetic** (Fasting glucose >100 on two or more blood draws or HgbA1C 5.7-6.4)
 - **Hypertension** (SBP > 140 or DBP >90 or on blood pressure medications or diagnosis of hypertension in medical record)
 - **Waist Circumference** > 40 inches for males or >35 inches for females
 - **Hyperlipidemia** (LDL >130, HDL <40 for males, HDL <50 for females, Triglycerides >200, on lipid lowering medications and/or diagnosis of hyperlipidemia in medical record)
- **Exclusion Criteria:**

- Males <35 years old
- Women <45 years old (please note the age difference is due to the fact that female plaque formation with calcification has been shown to lag that of males by about 10 years)
- Officer Rank – officers are excluded as we are looking at the enlisted culture in the military.
- History of any of the following:
 - Coronary Artery Disease (CAD)
 - Coronary Artery Bypass Grafting (CABG)
 - Myocardial Infarction (MI)
 - Percutaneous Intervention/Stent Placement (PCI)
 - Angina – cardiac chest pain
 - Radiotherapy (external beam, brachytherapy, radiopharmaceutical)

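### Secondary aim 1a compares CAC by metabolic syndrome with no adjustment, although the entry rule shapes the comparator group; the net direction of the error is unknown

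*Combined protocol and SAP*

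**What the plan says.** - Section 6.2, secondary aim 1a, sets up the contrast "Those meeting the criteria for metabolic syndrome vs. those not meeting criteria" and asks whether it is associated with calcified plaque. The definition is deferred to attachment 1, "Diagnostic Criteria for Metabolic Syndrome", which is not in the text available for this review.
- Section 6.6, Secondary Aims: "A t-test will be used to compare CAC scores between each group in the following categories". Metabolic syndrome is the first of three such categories. No covariate, adjusted model or sensitivity analysis is named for it.
- Section 6.7, Inclusion Criteria: "One or More of the Following Risk Factors". The five are smoking ("at least 5 pack years in the past 5 years"), diabetes or pre-diabetes, hypertension, waist circumference and hyperlipidemia. LDL above 130 meets the last one by itself.
- Section 6.1 sets smoking apart from the metabolic factors: "Smoking and sedentary lifestyle exacerbate the risk".
- Aim 2a is handled differently. Section 6.6 says "The correlation between CAC and FRS scores will be described using multiple linear regression for the following categories", and by section 6.4 (Measurements) the Framingham score (FRS) "includes age, systolic blood pressure, HDL level, Total Cholesterol level and smoking status".

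**The concern.** With the usual syndrome components (waist, blood pressure, glycaemia, HDL, triglycerides), a member with the syndrome will nearly always satisfy an entry criterion through the syndrome itself. A member without it enters only by having some qualifying factor. Two of those routes, smoking and high LDL, are not usual syndrome components but are plausible drivers of coronary calcium.

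The non-syndrome group is therefore not a general non-syndrome group. Part of the t-test contrast is syndrome versus enrolled as a smoker or for high LDL. Age, which the test also ignores, may differ between the groups as well. At stake is whether the result reported for aim 1a can be read as the association the aim asks about.

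**Working it through.** **1. What the plan's own numbers give.** The only sample-size calculation (6.6) is for prevalence: n = 1.96² × p(1 − p) / 0.05². At p = 0.085 this is 119.5, so 120. At p = 0.10 it is 138.3, which the plan gives as 138. Both reproduce. Nothing is calculated for aim 1a. Expected CAC-positive men number 138 × 0.10 = 13.8 to 138 × 0.206 = 28.4, about 14 to 28. The 20.6% is the male prevalence in the Army cohort cited in 6.1.

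**2. Enrichment of the comparator.** Let s, l and q be the proportions of non-syndrome members who smoke, have high LDL, or have another entry factor, taken as independent. Then P(eligible) = 1 − (1 − s)(1 − l)(1 − q), and the smoker share among those eligible is s / P(eligible).
- Take s = 0.30 (overall military rate in 6.1), with l = 0.30 and q = 0.40 assumed. P(eligible) = 1 − 0.7 × 0.7 × 0.6 = 0.706. Smokers rise from 30% to 0.30/0.706 = 42%, and high LDL likewise.
- With s from 21% to 40% (rates in 6.1), l from 20% to 40% and q from 20% to 60%, the enrolled smoker share is 26–65% and the high-LDL share 25–64%.

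**3. Effect of selection on the crude ratio.** Assume risk ratios of 1.5 for the syndrome, 1.5 each for smoking and LDL, and 1.3 for another entry factor, which every syndrome member carries. In units of baseline risk, for the same example:
- Syndrome: 1.5 × 1.15 × 1.15 × 1.3 = 2.579.
- All non-syndrome: 1.15 × 1.15 × 1.12 = 1.481.
- Enrolled non-syndrome: (1.481 − 0.294) / 0.706 = 1.682.

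The crude ratio falls from 2.579/1.481 = 1.74 to 2.579/1.682 = 1.53. With smoking and LDL ratios of 2.0 it falls from 1.74 to 1.46. Over the whole grid the enrolled ratio is 0.74 to 0.94 of its unselected value.

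**4. Simulation on the odds-ratio scale, no age effect.** Assumptions: five components at 20–25% prevalence with latent correlation 0.3, syndrome = three or more, smoking 15–25%, high LDL 30–35%, both independent of the syndrome. In the base setting the enrolled groups have 15% against 20.5% smokers and 30% against 41% high LDL. A true odds ratio of 2.0 for CAC above zero then reads, over repeat runs, as:
- 1.83–1.87 with smoking and LDL odds ratios of 1.5;
- 1.74 with odds ratios of 2;
- 1.56–1.59 with odds ratios of 3 and 25% smokers.

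Stratifying on smoking and LDL returns 1.98–2.01.

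**5. Adding age.** A second simulation assumes odds ratios of 1.8 (syndrome), 1.8 (smoking), 1.6 (LDL), 1.10 per year of age and 1.2 for another entry factor. That factor is present in 40% of members and in every syndrome member, and the syndrome in 30%. With smoking and LDL equal between groups before selection:

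| Syndrome group older by | Crude, all | Crude, enrolled | Enrolled, adjusted for smoking, LDL, age |
|---|---|---|---|
| 0 years | 1.94 | 1.67 | 1.92 |
| 2 years | 2.36 | 2.04 | 1.94 |
| 4 years | 2.82 | 2.45 | 1.95 |

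Letting smoking differ by ±5 points and LDL by up to 10 points, the enrolled crude value runs 1.63–1.84, 1.99–2.18 and 2.35–2.64 for the three age gaps. Selection lowers the crude value in all 18 scenarios, yet the crude value lies above the adjusted one whenever there is an age gap.

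**6. Partial adjustment.** Take the structure of step 4 with a 2-year age gap, 20% smokers, 33% high LDL and both odds ratios 2. A true 2.0 reads 2.05–2.10 crude, 2.35–2.41 adjusted for smoking and LDL only, and 1.99–2.03 with age added. A true 1.0 reads 1.21–1.23 with smoking and LDL only, and 1.01–1.02 with age added.

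**7. Sampling error.** With 138 men, 10–20.6% positive and 25–35% with the syndrome (assumed), the standard error of the log odds ratio is about 0.43–0.59. The shift in step 4 is ln(2.0/1.8) = 0.11 to ln(2.0/1.6) = 0.22, or 0.11/0.59 to 0.22/0.43: about 0.2 to 0.5 of a standard error.

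**The case against.** A reader might infer that the planned test is biased toward no difference, or would show a spurious protective effect when there is none. The documents do not support that as a net statement. Entry is open-ended from age 35 in men and 45 in women (6.7), and a 2-year age gap is enough to turn the error upward. If smoking and high LDL are each 10 points commoner with the syndrome and there is no age gap, the step 4 model gives a crude 1.99 for a true 2.0, so the attenuation vanishes. Only the selection component has a known direction.

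Nor can it be said that the rule removes members from the comparator alone. That needs every syndrome member to meet an entry cut-off, and the syndrome cut-offs were not available. Treating LDL as outside the syndrome is also an assumption: section 6.1 lists dyslipoproteinemia among the metabolic factors.

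Aim 2a should not be drawn in. It is planned as a multiple regression involving FRS, which already carries age, smoking and total cholesterol.

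Three further points stand:
- The declared population is members with at least one risk factor (6.2), so the crude difference is a valid description within it. It does not isolate the association asked about.
- The figures above are risk or odds ratios, mostly for CAC above zero, whereas the t-test uses the scores. In step 4, part of the gap from 2.0 (crude 1.89–2.00 before selection) is not due to the entry rule.
- The shift is smaller than sampling error, and the aim is secondary and unpowered.

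**Conclusion.** The point holds in limited form. Aim 1a asks about an association and has only an unadjusted test. The entry rule leaves the comparator with no member free of all five risk factors and, other things equal, with more smokers and high-LDL members. Taken alone, this selection would make a true odds ratio of 2.0 read as about 1.6 to 1.8. Age differences, or a positive link of smoking or LDL with the syndrome, can offset or reverse that. The net direction is unknown, and the unadjusted result does not isolate the association.

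The sizes rest on assumed effects, LDL prevalences and age gaps, and on the usual syndrome components. This is a worthwhile, inexpensive improvement to one secondary comparison; it does not affect the prevalence aim.

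**What to change.** In section 6.6:
- Keep the unadjusted comparison for aim 1a and label it descriptive.
- Add a regression of CAC on metabolic syndrome adjusted for age, sex, smoking and LDL (or lipid-lowering treatment). Smoking and LDL should not be entered alone, because leaving out age can move the estimate further from the truth (step 6).
- If CAC above zero is the outcome, use a penalised (Firth) fit. With 14 to 28 positive men and five terms, there are only 14/5 = 2.8 to 28/5 = 5.6 positive men per term.
- Tabulate these covariates by syndrome group beside the result, and state that every comparator member has at least one risk factor.

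The variables are already obtained through the interview, record check, laboratory tests and FRS inputs. The cost is a short addition to the plan, a few model terms and a wider interval.
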